#### 9.5.1.2 6-minute Walk Test

The 6MWT measures the distance a subject can quickly walk on a flat, hard surface in 6 minutes (6-minute walk distance). This test evaluates the global and integrated responses of all the systems involved during exercise, including the pulmonary and cardiovascular systems, systemic circulation, peripheral circulation, blood, neuromuscular units and muscle metabolism. The 6MWT will be performed according to ATS guidelines for the 6MWT [Lancaster, 2018; ATS Guidelines, 2002].

# 9.5.1.3 Titrated Oxygen Requirement

Oxygen titration will be performed to determine the lowest oxygen flow rate required to maintain an oxygen saturation ( $S_{p,O2}$ ) of  $\geq 96\%$  in the standing position (TOR). Titration will begin with the subject breathing room air.  $S_{p,O2}$  will be monitored for 1 minute. If the  $S_{p,O2}$  is  $\geq 96\%$ , the test

PRIVATE AND CONFIDENTIAL INFORMATION OF HORIZON THERAPEUTICS IRELAND DAC (A WHOLLY OWNED SUBSIDIARY OF AMGEN INC.)

Page 79 of 153

will conclude. If  $S_{p,O2}$  is <96%, the oxygen flow rate will be increased each minute to achieve a target  $S_{p,O2}$  of  $\geq$ 96% using the following titration steps: 1, 2, 3, 4, 5, 6, 8, 12, and 15 L·min.

# 9.5.1.4 Diffusing Capacity of the Lungs for Carbon Monoxide

The site will use its own DLCO equipment and conduct all measurements with the same DLCO equipment in case that several devices are available at the site. Single-breath DLCO measurement will be performed according to the ATS guideline on DLCO measurements, when possible [Graham et al., 2017]. Refer to the DLCO procedural manual for details. Sites may request, but will not be required, to have subjects attend unscheduled visits for repeat DLCO measurements when the initial measurement has not passed according to DLCO central review quality control criteria. DLCO assessments for determining subject eligibility for the trial can be repeated once during the 35-day Screening window. During the treatment period, repeat measurements should be attempted within 1 week, if possible. DLCO results that do not pass quality control and for which it is not practical to recall the subject to the trial site for a repeat test, Investigators should assess and record within the subject's source documents whether the DLCO performed was valid per the site's standard practices and correlates well with the subject's clinical conditions and previous DLCO results.

DLCO values will be adjusted for altitude when necessary, and the most recent hemoglobin value. An adjustment for carboxyhemoglobin will be made if the Investigator determines that the subject may have elevated carboxyhemoglobin. The DLCO assessment should always be performed after the FVC measurement and should always be started approximately the same time each day.

### 9.5.1.5 Lung High-resolution Computed Tomography

Lung HRCT will be reviewed by a central reader. These results must be available prior to randomization.

If HRCT has been performed for clinical care in the 6 months prior to Screening and has been reviewed and deemed acceptable per central reader, then HRCT need not be performed at Screening.

# 9.5.1.6 Patient-reported Outcome Assessments

Health outcomes assessments are recommended to be administered at the beginning of the visit prior to collection of blood for analysis and other scheduled assessments.

A copy of each assessment is provided in the Appendix (Section 17).

#### **9.5.1.6.1** Living with IPF

The L-IPF is a validated questionnaire that assesses symptoms, disease impacts and health-related quality of life in subjects with IPF [Swigris et al., 2020]. This questionnaire was developed with input from the FDA and comprises 2 modules: a 15-item symptom module with 3 domains (dyspnea, cough, and energy), all with a 24-hour recall, and a 20-item impacts module

with 1-week recall. All items in both modules have response options in a 5-point (0-4) numerical rating scale format.

# 9.5.1.6.2 King's Brief Interstitial Lung Disease Questionnaire

The K-BILD is a self-completed health status questionnaire comprising 15 items and a 7-point Likert response scale that was developed and validated specifically for patients with IPF [Patel et al., 2012]. This questionnaire has 3 domains: psychological, breathlessness and activities and chest symptoms. The K-BILD domains and total score range from 0 to 100; 100 represents best health status. The K-BILD scoring has recently changed with the introduction of a logit transformation step. The minimal clinically important difference for the K-BILD total score (logit version), as determined by both anchor and distribution-based methods, is a change of 5 units [Sinha et al., 2019].

# 9.5.1.6.3 Leicester Cough Questionnaire

The LCQ is a patient-reported questionnaire evaluating the impact of cough on quality of life. This questionnaire was originally developed for use in people with idiopathic chronic cough and has since been validated for use in people with bronchiectasis and chronic obstructive pulmonary disease [Birring et al., 2003].

The LCQ comprises 19 items and takes 5 to 10 minutes to complete. Each item assesses symptoms or the impact of symptoms over the last 2 weeks on a 7-point Likert scale. Scores in 3 domains (physical, psychological, and social) are calculated as a mean for each domain (range: 1 to 7). A total score (range: 3 to 21) is also calculated by summing the domain scores. Higher scores indicate better quality of life.

#### 9.5.1.6.4 SF-12 Health Survey

The SF-12 [Ware et al., 1996] is a 12-item survey used to assess general health-related quality of life. The SF-12 items are scored to generate a physical component score and mental component score (from the subject's perspective. The SF-12 examines 8 domains of health outcomes, including physical functioning, role-physical, bodily pain, general health, vitality, social functioning, role-emotional, and mental health. The SF-12 is a shorter version of the SF-36, which has accepted validity for use in subjects with IPF [Swigris et al., 2010; Tomioka et al., 2007] and is 1 of 4 questionnaires used in the IPF Prospective Outcomes, an ongoing observational US registry of patients with confirmed IPF that records patient-reported outcomes.

#### 9.5.2 Pharmacokinetic Measurements

Blood samples will be collected from all subjects to evaluate the PK of fipaxalparant (HZN-825) at the time points shown in Table 9.2. For visits with post-dose PK samples, the morning dose regimen will be taken in the clinic. Note that all pre-dose samples will be collected prior to any trial drug administration during the clinic visit. For subjects not entering the 52-week Extension Phase, a sample will be collected anytime during the Week 52 Visit. PK sample collection time

and the most recent dosing time prior to PK sample collection will be recorded for all PK samples.

If the clinic visit is in the morning, on days when a pre-dose PK sample will be collected, subjects will be instructed to withhold taking trial drug before the visit, and drug and a meal will be administered in the clinic after the pre-dose PK samples are taken. Time of drug administration in the clinic as well as the most recent dosing time prior to the visit will be recorded; 1 additional PK sample will be collected 2 to 4 hours after dosing in the clinic during the Week 16, Week 28, and Week 56 Visits.

If the clinic visit is in the afternoon, on days when a pre-dose PK sample will be collected, subjects will be instructed to take trial drug before 8 a.m. with a meal and record dosing time; 1 PK sample will be collected anytime during the clinic. For the Week 16, Week 28, and Week 56 Visits, subjects will receive the evening dose during the visit (dosing time to be recorded) if it is at least 8 hours from the morning dosing. An additional PK sample will be collected 2 to 4 hours post-dose; otherwise, subjects will be instructed to take the evening dose at regular dosing time and no post-dose PK sample will be collected.

Instructions for collection, processing, handling, storing and shipping of PK samples will be detailed in a laboratory manual that will be provided to each site prior to site initiation.

**Table 9.2** Schedule of Pharmacokinetic Sample Collection

Time point	Pre-dose	2 to 4 Hours Post-dose	Anytime During Visit
Core Phase			
Day 1		X	
Week 4	X		
Week 10			X
Weeks 16 and 28	X	X	
Weeks 40 and 52	X		
Extension Phase			
Day 1 (Week 52 of Core Phase)	X		
Week 56	X	X	
Week 68	X		
Week 80	X		
Week 92	X		

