Urinalysis 18		X	X		X		X	X	X	X	X	X	X	X	X
HBV and HCV serology		X													
HIV test 		X													
Adverse event assessment 22		X	X	X	X	X	X	X	X	X	X	X	X	X	X
Prior/concom. medications 		X	X	X	X	X	X	X	X	X	X	X	X	X	X
PK samples 			X		X		X	X		X		X		X	
Pharmacodynamic serum sample (collect pre-dose) 			X					X		X				X	
Pharmacogenetic sample (optional) 			X												
PBMC sample 			X							X				X	

6MWT=6-minute Walk Test; BID=twice daily; concom.=concomitant; CYP=cytochrome P450; DLCO=diffusing capacity of the lungs for carbon monoxide; FVC=forced vital capacity; HBV=hepatitis B virus; HCV=hepatitis C virus; HIV=human immunodeficiency virus; HRCT=high-resolution computed tomography; hsCRP=high-sensitivity C-reactive protein; IPF=idiopathic pulmonary fibrosis; LCQ=Leicester Cough Questionnaire; L-IPF=Living with IPF; K-BILD= King's Brief Interstitial Lung Disease Questionnaire; LPAR1=lysophosphatidic acid receptor 1; PBMC=peripheral blood mononuclear cell; PD=premature discontinuation; PK=pharmacokinetic; QD=once daily; SARS-CoV-2=severe acute respiratory syndrome coronavirus 2; SF-12=SF-12® Health Survey; SLCO=solute carrier organic anion transporter family member; W=Week; WOCBP=women of childbearing potential

- 1. Screening procedures can take place over more than 1 day/clinic visit provided consent is obtained first and all assessments are completed within the designated window. An abnormal test or assessment during Screening may be repeated once during the Screening Period.
- 2. On Day 1 (Baseline), subjects will be randomized and receive the first dose of trial drug in the clinic. All Day 1 assessments should be performed before the first dose of trial drug is administered in the clinic except for the PK sample collected 2-4 hours post dose.
- 3. Subjects should fast at least 8 hours prior to clinic visits on Day 1, Week 28, and Week 52 due to the need for fasting glucose, total cholesterol, high-density lipoprotein cholesterol, low density lipoprotein cholesterol, and triglycerides.
- 4. Remote (telephone) visit.

PRIVATE AND CONFIDENTIAL INFORMATION OF HORIZON THERAPEUTICS IRELAND DAC (A WHOLLY OWNED SUBSIDIARY OF AMGEN INC.)

Date: 07 October 2024

IND 154671

- 5. Visits may be conducted as home health visits, as available within local regions.

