- 16. Vital signs (blood pressure, heart rate, respiratory rate, temperature, pulse oximetry) will be measured at each visit.
- 17. Additional electrocardiograms or echocardiograms will be conducted, if clinically indicated. An echocardiogram that has been performed within 3 months prior to Day 1 can serve as the Baseline echocardiogram if the subject has been clinically stable.
- 18. See Section 9.5.5.9 for details.
- 19. For subjects taking warfarin, physicians should monitor their INR, as needed.
- 20. Includes fasting glucose, total cholesterol, high-density lipoprotein cholesterol, low-density lipoprotein cholesterol, and triglycerides.
- 21. HIV testing is optional based on Investigator assessment, institutional practices or local guidelines to rule out suspected HIV or potential for a positive HIV result. Subject consent is required prior to HIV testing.
- 22. Adverse events that occur after signing the informed consent form and prior to dosing on Day 1 will be considered medical history. Adverse events occurring or worsening after the first dose of trial drug through the Safety Follow-up Visit will be considered treatment-emergent adverse events. All adverse events that occur from the signing of informed consent through the Safety Follow-up Visit will be recorded.
- 23. Includes recording of herb/supplement use. See Table 9.1 for restrictions regarding medications.
- 24. PK samples will be collected at each of the following visits: Day 1 (at 2 to 4 hours after the first dose of trial drug), Week 4 (pre-dose), Week 10 (anytime during the visit), Weeks 16 and 28 (pre-dose and 2 to 4 hours post-dose), and Weeks 40 and 52 (pre-dose for subjects entering the 52-week open-label Extension Phase). For the Day 1, Week 16 and Week 28 Visits with post-dose PK samples, the morning dose regimen will be taken in the clinic. Note: all pre-dose samples will be collected prior to any trial drug administration during the clinic visit; record date and time of last dose prior to visit. For subjects not entering the 52-week open-label Extension Phase, a sample will be collected anytime during the Week 52 Visit. Record date/time of all samples.
- 25. To be stored for future analysis. Use of stored serum sample for pharmacodynamic endpoints will be limited to understanding the trial drug as related to investigation of the LPAR1 pathway or disease for the current trial.

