# 2.2 Schedule of Assessments During the Extension Phase

		Safety Follow-up Visit									
											4 weeks after last dose of fipaxalparant (HZN-825)
Trial Visit	13	14	15	16	17 W74 	18	19 W86 	20 W92	21	22 W104/PD 	23
Trial Week (W) Visit Window (±days)	W52  (±7)	W56	W62	W68 (±7)		W80	(±7)	(±7)	W98 		(114)
Informed consent 4	(±1) X	(±5)	(±7)	(±/)	(±7)	(±7)	(±/)	(±/)	(±7)	(±7)	(±14)
	X										
Review eligibility criteria	X 5					X				X	
Weight Fipaxalparant (HZN-825) dispensing		37	37	37				37		Λ	
	X	X	X	X		X		X			
Compliance	X	X	X	X	X	X	X	X	X	X	
Efficacy Assessments			ı	1					ı		
FVC % predicted/spirometry 	X 5			X		X		X		X	
Titrated oxygen requirement	X 5					X				X	
6MWT	X 5					X				X	
Lung HRCT	X 5									X 7	
DLCO	X 5, 8					X 8				X 8	
Patient-reported Outcome Assessmen											
L-IPF, K-BILD, LCQ, SF-12	X 5					X				X	
Anchor questions											
FVC (last week)	X 5					X				X	
FVC (change since start of trial)						X				X	
Clinical Safety Assessments											
Pregnancy test 	X 5	X	X	X		X		X		X	X
Physical examination 	X 5	X	X	X		X		X		X	X
Vital signs, including pulse oximetry 11	X 5	X	X	X		X		X		X	X
Orthostatic hypotension assessment	X 5	X				X				X	
12-lead electrocardiogram 	X 5	X				X				X	
Echocardiogram 	X 5										
Clinical Laboratory Safety Tests											
Chemistry and hematology 	X 5	X	X	X		X		X		X	X
Fasting glucose and lipids 	X 5					X				X	
hsCRP	X 5					X				X	
Urinalysis 	X 5	X	X	X		X		X		X	X

PRIVATE AND CONFIDENTIAL INFORMATION OF HORIZON THERAPEUTICS IRELAND DAC (A WHOLLY OWNED SUBSIDIARY OF AMGEN INC.)

IND 154671

Fipaxalparant (HZN-825) Protocol: HZNP-HZN-825-303 Version 5.0, Amendment 4

		Open-label Treatment Period											
											4 weeks after last dose of fipaxalparant (HZN-825)		
Trial Visit	13	14	15	16	17	18	19	20	21	22	23		
Trial Week (W)	W52 	W56	W62	W68	W74 	W80	W86 	W92	W98 	W104/PD 			
Visit Window (±days)	(±7)	(±5)	(±7)	(±7)	(±7)	(±7)	(±7)	(±7)	(±7)	(±7)	(±14)		
PK samples 	X 5	X		X		X		X					
Pharmacodynamic serum sample (collect pre-dose) 18	X 5					X				X			
PBMC samples (collect pre-dose) 19	X 5					X				X			
Adverse event assessment	X	X	X	X	X	X	X	X	X	X	X		
Prior/concomitant medications 	X 5	X	X	X	X	X	X	X	X	X	X		

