# 9.5.1 Efficacy Variables

#### **9.5.1.1 Spirometry**

Spirometry, including FVC % predicted, will be assessed using a device provided by the Sponsor. Spirometry should only be performed by a trained assessor and the same assessor should complete the procedure for a given subject throughout the duration of the trial, unless it is not possible. For spirometry at Screening, the central review results are required for determination of eligibility.

Spirometry measurements must be performed according to ATS/ERS 2019 guidelines [Graham et al., 2019] whenever possible. The test will be done in triplicate (3 curves to be provided) and the best result selected according to the guidelines. The best of 3 efforts will be defined as the highest FVC, obtained on any of the 3 blows meeting the ATS/ERS criteria with a maximum of 8 maneuvers.

Spirometry measurements should be attempted at approximately the same time of day from Baseline onwards. On days of clinic visits, subjects must refrain from strenuous activity at least 12 hours prior to pulmonary function testing. Smoking should be discouraged throughout the visit days and will not be permitted in the 30-minute period prior to spirometry. Subjects should also avoid cold temperatures, environmental smoke, dust or areas with strong odors (e.g., perfumes). If treated with bronchodilators, washout of 24 hours for long-acting and 8 hours for short-acting bronchodilators should be observed before spirometry.

Spirometry results will be electronically transmitted. To ensure the quality of primary endpoint measurement, a central spirometry review will occur. Results will be over-read by a central reader, confirmed by the clinical site and data will be transferred into the clinical database.

In addition, the subject will be asked the following anchor (additional) questions at the time points indicated in Section 2.1 and Section 2.2.

Rate the severity of your breathing problems over the last week:

- 0: no breathing problems
- 1: mild breathing problems
- 2: moderate breathing problems
- 3: severe breathing problems
- 4: very severe breathing problems

How have your breathing problems changed since the start of the trial?

- +3: very much better
- +2: much better
- +1: a little better
- 0: no change
- -1: a little worse
- -2: much worse
- -3: very much worse

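### For afternoon visits, Protocol 9.5.2 tells subjects to eat with their morning dose but does not tie that meal to the fasting glucose and lipid draws at Weeks 28, 52 and 80

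*Protocol*

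**What the plan says.** **The fast.** Protocol Section 2.1, footnote 3: "Subjects should fast at least 8 hours prior to clinic visits on Day 1, Week 28, and Week 52". The reason given is the fasting glucose and lipid panel, which the Core schedule places at those three visits. In Section 2.2 the row "Fasting glucose and lipids" is marked at Weeks 52, 80 and 104. The Extension footnotes list the tests in the panel but give no number of hours.

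**The meal.** Section 9.5.2 treats pre-dose PK days in two ways:

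- Morning visit: the subject holds the dose at home, and drug and a meal are given in clinic after the pre-dose sample.
- Afternoon visit: "subjects will be instructed to take trial drug before 8 a.m. with a meal and record dosing time". At Weeks 16, 28 and 56 the evening dose is given in clinic if 8 hours have passed since the morning dose; "otherwise, subjects will be instructed to take the evening dose at regular dosing time and no post-dose PK sample will be collected".

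**Which days are pre-dose PK days.** Footnote 24 and Table 9.2 make Week 28 one for everyone. Footnote 24 makes Week 52 one only for subjects continuing into the Extension; the others may give that sample at any point in the visit. Table 9.2 also lists Week 80 as pre-dose. Day 1 has only a post-dose sample, and Week 104 has none.

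**Where the Week 28 dose is taken.** Section 9.5.2 also says: "For visits with post-dose PK samples, the morning dose regimen will be taken in the clinic". Footnote 24 names the visits: "For the Day 1, Week 16 and Week 28 Visits with post-dose PK samples, the morning dose regimen will be taken in the clinic".

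**Analysis.** SAP Section 7.2, Table 3, lists lipids and fasting lipids, and has one glucose entry under Chemistry. The SAP does not say how a sample is assigned to a fasting summary. Safety outcomes are summarised descriptively (Protocol 9.6.1.6; SAP Section 7).

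**The concern.** A subject with an afternoon Week 28 visit can follow 9.5.2 exactly and still arrive having eaten within 8 hours. The glucose and lipids drawn at that visit are scheduled as fasting but would be fed samples. Neither document says which instruction gives way. The meal cannot simply be dropped, because the drug is to be taken with a meal throughout.

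What is at stake is the meaning of the fasting glucose and lipid summaries. For Extension entrants the Week 52 result is the OLE Baseline, so a fed value there also enters the changes to Weeks 80 and 104. Week 80 can itself be a fed sample, so both ends of that change may be affected.

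**Working it through.** No power, alpha or event figure is involved. The check is a comparison of the schedules plus clock arithmetic.

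**1. Where the two rules meet**

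| Fasting draw | Pre-dose PK day? | Afternoon meal instruction applies? | Fast stated? |
|---|---|---|---|
| Day 1 | No; first dose in clinic | No | 8 h |
| Week 28 | Yes, all subjects | Yes | 8 h |
| Week 52 | Yes, Extension entrants only | Yes, for them | 8 h |
| Week 80 | Yes (Table 9.2) | Yes | No duration |
| Week 104 | No PK sample | No | No duration |

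So 2 of the 3 Core fasting draws carry a direct conflict. Over both phases the afternoon instruction reaches 3 of the 5 scheduled fasting draws (Core Day 1, 28, 52; Extension 80, 104; 3 + 2 = 5).

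**2. When both rules can be kept**

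The condition is visit start ≥ meal time + 8 h. Footnote 3 counts to the visit; if blood is drawn later in the visit, the fast to the draw is longer by that delay.

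| Visit start | Latest meal that keeps the fast |
|---|---|
| 12:00 | 04:00 |
| 13:00 | 05:00 |
| 14:00 | 06:00 |
| 15:00 | 07:00 |
| 16:00 | 08:00 |

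Section 9.5.2 gives only a latest time for the meal. A subject who uses that limit and eats just before 08:00 meets the fast only at about 16:00 or later.

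**3. Size of the shortfall at one visit time**

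Meal between 06:00 and 08:00 (assumed; the documents give no earliest time), visit at 13:00:

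- fast: 13:00 − 08:00 = 5 h, up to 13:00 − 06:00 = 7 h
- shortfall: 8 − 7 = 1 h, up to 8 − 5 = 3 h

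**4. Does the protocol foresee such visits?**

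Yes, at Week 28. The branch of 9.5.2 that omits the post-dose sample exists for visits where the evening dose would fall under 8 hours after the morning dose. That 8-hour condition governs dosing, not eating. At Weeks 52 and 80 the section has no 8-hour condition at all.

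**5. Is it reconciled elsewhere?**

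Protocol 9.5.5.9 repeats that fasting tests are done and gives no meal timing. Footnotes 3, 20 and 24 and the SAP's copy of the schedule give no order of precedence.

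**The case against.** **The rules are not always incompatible.** A reader might infer a contradiction at every afternoon visit, or a firm cut-off at 14:00. Neither is supported. An early meal or a late visit satisfies both rules, the morning path raises no conflict, and 14:00 follows only if nobody eats before 06:00. What stands is that 9.5.2 permits a meal up to 08:00 for a visit at any time in the afternoon.

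**Other text points the other way.** Section 9.5.2 and footnote 24 put the Week 28 morning dose in the clinic, and Extension footnote 17 has pre-dose samples taken before any drug that day. A site following those would not dose at home first. But the afternoon paragraph tells it to, and nothing ranks the instructions. This leaves the site with more to resolve.

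**A rule may exist elsewhere.** Section 9.5.5.9 refers to laboratory instructions supplied separately. Those, the eCRF and the TLF shells are not available here and may record fasting status. SAP Table 3 separates lipids from fasting lipids, which is compatible with that. Its single glucose entry sits in the routine chemistry panel and does not show that fed and fasting glucose are pooled. So mislabelled results are a possibility and are not demonstrated; the gap in the protocol text remains.

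**The stakes are small.** This is correct. Glucose and lipids are not efficacy endpoints, the AESI, or among the protocol's listed important risks. All three blinded arms take tablets morning and evening, so the instruction favours none of them.

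**Stronger readings.** One might infer a threat to FVC or the interim analysis; neither uses these tests. One might infer PK loss; samples not counted as pre-dose on the afternoon path result from 9.5.2 and the SAP's 10–14 hour window, not from the fast. One might infer that all Extension laboratory changes are compromised; only these tests are involved, and changes are also summarised from HZN-825 Baseline, which SAP 2.5 takes before the first Core dose.

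**Conclusion.** The point holds in limited form. At Week 28 for all subjects, and at Week 52 for Extension entrants, the afternoon instruction conflicts with the 8-hour fast whenever the visit starts less than 8 hours after the meal. At Week 80 the same instruction applies and no fasting duration is stated, so there the problem is an undefined fast rather than two clashing numbers.

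The consequence is limited to descriptive fasting glucose and lipid summaries at those three visits, and to changes from OLE Baseline at Weeks 80 and 104 for the same tests. Efficacy, the interim analysis and the hypothesis tests are unaffected.

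The 16:00 figure needs only the text (a meal just before 08:00). The 1 to 3 hour shortfall rests on an assumed meal between 06:00 and 08:00 and a 13:00 visit. The number of affected subjects is unknown, because the documents do not give the share of afternoon visits. Severity: minor. Confidence is high on the text, lower on whether any result is actually mislabelled.

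**What to change.** **Protocol 9.5.2, one clause**, for example: at visits with fasting glucose and lipids (Weeks 28, 52 and 80), use the morning path where the subject's usual visit time allows; for an afternoon visit, drug and meal must be completed at least 8 hours before the fasting draw; otherwise record the sample as non-fasting.

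**Protocol 2.2, footnotes:** state the same 8-hour fast for the Extension fasting draws.

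**SAP 7.2, one sentence:** samples recorded as non-fasting are left out of the fasting glucose and lipid summaries. For samples already taken, the dosing times that 9.5.2 requires can help to classify them, since the drug is taken with the meal.

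The allowance for usual visit time matters. Section 9.5.1.1 says "Spirometry measurements should be attempted at approximately the same time of day from Baseline onwards", and Weeks 28 and 52 are also spirometry visits. Moving an afternoon subject to the morning at those visits alone would cut against that. Moving all six Core spirometry visits (Day 1, Weeks 4, 16, 28, 40 and 52) to the morning would be out of proportion to a few descriptive laboratory draws, and too late for subjects whom SAP 2.5 already describes as enrolled.

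**Cost:** a few lines of text, a fasting-status entry if the eCRF has none, slightly less scheduling freedom, and a few samples left out of the fasting summaries.
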